4.8.4. Missing Data

Analyses of efficacy and safety will be based on available cases, without imputation for missing values.

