3.4. SAFETY PLAN

The safety assessments to be conducted for this study are listed in Section 4.5.

The safety and tolerability of intravitreal ranibizumab injections have been investigated in previous Phase I, I/II, III, and IIIb studies in AMD, RVO, and DME trials. Potential safety issues associated with the route of administration or the pharmacology of ranibizumab in the study population include decreased BCVA, intraocular inflammation, intraocular infection, transient and/or sustained elevation of intraocular pressure (IOP), cataract development or progression, retinal or intravitreal hemorrhage, macular edema, retinal break or detachment, and arterial thromboembolic events (ATEs). Safety will be assessed by visual acuity, ophthalmic examinations, fluorescein angiograms, B-Scans, OCT, intraocular pressure, vital signs, and adverse event documentation.

To minimize the risks of intraocular infections, all injections will be performed employing sterile techniques as described in Appendix B. Study drug administration will be held for subjects who experience certain ocular events or infections. In the event any subject develops an adverse event in the study eye that is considered by the evaluating physician to be severe in intensity, serious consideration should be given to withdrawing the subject from the study.

The PI or designated Sub-Investigators will review all adverse events on an ongoing basis to determine causality and relationship to study drug and/or study procedures.

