4.5.1.2. Efficacy Procedures

Best Corrected Visual Acuity (Performed at every visit)

Visual function of the study eye and fellow eye will be assessed using the ETDRS protocol (The Early Treatment Diabetic Retinopathy Study Group, 1985) at 4 meters at every visit.

**See Appendix H for Visual Acuity Testing Protocol*

Intraocular Pressure (Performed at every visit)

Intraocular pressure (IOP) of both eyes will be measured pre-dose at every visit. IOP of the study eye will be measured 30 minutes (\pm 15 minutes) post-dose. The method used for IOP measurement for a subject must remain consistent throughout the study.

Slit Lamp Examination (Performed at every visit)

Subject's anterior eye structure and ocular adnexa of both eyes will be examined at every visit using a slit lamp, pre-dose, by the PI or Sub-Investigator.

Indirect Ophthalmoscopy (Performed at every visit)

Subject's posterior pole and peripheral retina will be examined by indirect ophthalmoscopy at every visit, pre-dose by the PI or Sub-Investigator.

Optical Coherence Tomography (OCT) (Performed at every visit)

Ocular morphology will be evaluated at every visit using the Heidelberg Spectralis SD-OCT. Starting with the screening visit, images will be captured for both eyes. All OCTs will be electronically archived at the site as part of the

source documentation. Optical coherence tomography technicians must provide previous certification by a reading center, within the last 2 years, or provide evidence of proper training to ensure consistency and quality in image acquisition.

*See Appendix D for OCT protocol

Fundus Photography/Fluorescein Angiography

The anatomical state of the retinal vasculature will be evaluated using Fundus Photography (FP) and wide field Fluorescein Angiography (FA). FP and FA will be captured for both eyes. All FPs and FAs will be archived at the site as a part of source documentation. Photographers must provide previous certification by a reading center, within the last 2 years, or provide evidence of proper training to ensure consistency and quality in image acquisition.

FP and FA evaluations will be performed at screening, Week 24, Week 36, Week 48, Week 78, and Week 104 or Early Termination visit.

* See Appendix D for Imaging Protocol

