4.6. SUBJECT DISCONTINUATION

Subjects have a right to withdraw from the study at any time.

The subject may be withdrawn from the study for any reasons: if it is in the best interest of the subject, concurrent illness, adverse events, or worsening condition. Retina Consultants of Houston or the Principal Investigator may request the withdrawal of a subject because of protocol violations, administrative reasons, or any other valid and ethical reasons.

If a subject discontinues from the study, he or she will not be allowed to re-enter the study.

Reasons for subject discontinuation may include, but are not limited to, the following:

- Sensory rhegmatogenous retinal detachment or Stage 3 or 4 macular hole
- Investigator determination that it is not in the best interest of the subject to continue participation

- Pregnancy
- Need for anti-VEGF therapy other than ranibizumab in the study eye, unless as a part of the prospective investigational study design
- SAE
- Any other safety concerns

In the event of an adverse event in the study eye that is considered by the investigator to be severe in intensity, serious consideration should be given to discontinuing the subject from the study.

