6. ANALYSES

All outcomes will be presented using descriptive statistics. For comparison of groups for primary and secondary outcomes, variables of interest will be statistically analyzed using analysis of variance (ANOVA), Student's t-tests, Chi square and Fisher's exact test. ETDRS data will be obtained for all visits

for all 40 of the participants. Bonferroni correction was applied to all pairwise comparison analyses for this study.

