6.1 Primary Outcome

The primary analysis will compare cohorts (A vs. B vs. C) on their mean change in ETDRS BCVA from baseline to week 48 and week 104 with the above described statistical tests. Adverse events will be reported using counts and percentages for each cohort.

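### The primary BCVA comparison drops any subject without a week-48 or week-104 value, although earlier BCVA could be used; selective loss is plausible, not shown

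*Protocol*

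**What the plan says.** **Missing data.** Protocol 4.8.4 gives one rule: "Analyses of efficacy and safety will be based on available cases, without imputation for missing values".

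**Analysis.** SAP 6.1 states: "The primary analysis will compare cohorts (A vs. B vs. C) on their mean change in ETDRS BCVA", from baseline to week 48 and to week 104. SAP 6 lists the methods for group comparisons: ANOVA, Student's t-tests, chi-square and Fisher's exact test, with a Bonferroni correction for pairwise comparisons. It names no repeated-measures model, no use of intermediate BCVA and no sensitivity analysis.

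**Completeness.** SAP 6 also says "ETDRS data will be obtained for all visits" for all 40 participants. It does not say what happens if they are not obtained.

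**Withdrawal.** Protocol 4.6 lists, among the reasons for withdrawal, "concurrent illness, adverse events, or worsening condition", and adds: "If a subject discontinues from the study, he or she will not be allowed to re-enter the study". For a study-eye adverse event judged severe, Protocol 3.4 says "serious consideration should be given to withdrawing the subject from the study", and 4.6 repeats the advice. Other grounds in 4.6, such as pregnancy or administrative reasons, have no evident link to acuity.

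**Data collected.** Protocol 4.5.1.2 and Appendix A schedule BCVA at every visit. Protocol 4.5.2 gives the early-termination visit the same assessments as the final visit. In year 2 the visit interval is individualised up to 12 weeks, with weeks 78 and 104 mandatory (Protocol 3.2 and Appendix A).

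**The concern.** An ANOVA or t-test on change to a fixed week uses only subjects with a value at that week. A subject who leaves at week 40 contributes nothing to the week-48 comparison, even with about ten BCVA measurements on file. The early-termination BCVA has no stated use.

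If those who leave tend to be the eyes doing badly, the remaining eyes look better than the cohort did. The within-cohort mean change, which is how Protocol 3.3.1 and 4.8.3.1 word the endpoint, is then too favourable. The comparison between cohorts is distorted only if selective loss is heavier in one cohort than in another. The cohorts differ in laser and injection schedule, so this could happen, but the withdrawal wording is the same for all three.

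The arms are small. In Cohort A two losses are 2/8, a quarter of the arm.

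**Working it through.** There is no planned figure to reproduce. The documents give no SD, no correlation between visits and no expected dropout. The sample size in SAP 2.1 (41 calculated, 40 enrolled) comes without an effect size or SD. The one completion figure is in Protocol 1.3: 7 of 10 patients completed an earlier ranibizumab study. It has no split by arm and no link to acuity. What follows is an illustration.

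**Step 1: one cohort, by counts.** If k of n eyes are lost and did D letters worse than those retained, the observed mean is too favourable by kD/n. Take D = 15 as an assumption (15 letters is also the loss threshold in Protocol 4.8.3.3) and k = 2:
- Cohort A: 2 × 15/8 = 3.8 letters
- Cohort B or C: 2 × 15/16 = 1.9 letters

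**Step 2: difference between two cohorts of 16.** Assume that change is normal with mean 0 and SD 15 at weeks 48 and 104, with correlation r = 0.7. A fraction p of eyes below −10 letters withdraws, and 5% of the others.

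Total loss T = 0.05 × Φ(10/SD) + p × Φ(−10/SD).

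Mean shift among those retained = (p − 0.05) × SD × φ(10/SD)/(1 − T).

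At SD 15, φ(0.667) = 0.3194 and Φ(−0.667) = 0.2525.

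| p | T | Shift in letters |
|---|---|---|
| 0.80 | 23.9% | 0.75 × 15 × 0.3194/0.7606 = 4.72 |
| 0.29 | 11.1% | 0.24 × 15 × 0.3194/0.8894 = 1.29 |
| 0.40 | 13.8% | 0.35 × 15 × 0.3194/0.8616 = 1.95 |
| 0.20 | 8.8% | 0.15 × 15 × 0.3194/0.9121 = 0.79 |

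The standard error of a 16 vs 16 difference is 15 × √(2/16) = 5.3 letters. If the week-104 value itself drives the loss, the week-104 difference is off by the difference in shifts. If the week-48 change drives it, multiply by r.

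| Case | Week-104 value drives loss | Week-48 change drives loss |
|---|---|---|
| Moderate (40% vs 20%) | 1.95 − 0.79 = 1.16 letters, 0.22 SE | × 0.7 = 0.81 letters, 0.15 SE |
| Extreme (80% vs 29%) | 4.72 − 1.29 = 3.43 letters, 0.65 SE | × 0.7 = 2.40 letters, 0.45 SE |

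With the same fractions, the same formula over SD 12 to 18 and r 0.5 to 0.85 gives:
- Moderate: 0.8 to 1.5 letters (week-104 value) and 0.4 to 1.3 (week-48 change)
- Extreme: 2.3 to 4.6 and 1.1 to 3.9

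If both cohorts have the same p, the difference is zero, although each mean is still shifted.

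**Step 3: what a likelihood model recovers.** Such a model in effect predicts the missing week-104 mean from observed week-48 values.
- *Loss depends on the observed week-48 change.* The bias is removed. With 4,000,000 simulated subjects per cohort, 0.02 letters or less remained in either case. In 20,000 simulated trials of 16 vs 16 in the extreme case, the available-case bias was 2.36 letters against −0.02 for the likelihood estimate, and the root-mean-square error was 6.06 against 5.66.
- *Loss depends on the unobserved week-104 value.* Only part is removed. With a known slope the remainder is (1 − 0.7²) × 3.43 = 1.7 letters (extreme) and 0.51 × 1.16 = 0.6 (moderate). Estimating the slope from completers leaves 1.9 to 2.1 letters in the extreme case and still about 0.6 in the moderate one.

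**The case against.** **The no-imputation rule is not itself at fault.** A likelihood repeated-measures model also uses available data and imputes nothing, so Protocol 4.8.4 permits it. This stands. The gap arises because SAP 6 and 6.1 name only single-timepoint tests. It is an analysis choice that can be improved, not a contradiction between the documents.

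**The SAP expects complete data.** If BCVA were obtained at all visits for all 40, nothing would be lost. That sentence states an intention. Protocol 4.5.2 and 4.6 provide for early withdrawal without re-entry, and no rule covers the case where the intention fails.

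**The harm is hypothetical and may be small.** A reader might infer that poor-outcome eyes will be lost, or that the A vs B vs C comparison is biased. The documents support neither. Worsening condition is not defined by acuity, several grounds are unrelated to it, and nothing shows that loss will differ between cohorts. A moderate imbalance of 0.15 to 0.22 SE would raise a nominal two-sided 5% error rate only to about 5.3 to 5.6%. The extreme case needs four in five of the poorly performing eyes in one cohort to leave. This limits the severity of the point.

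**A larger model in 40 subjects has its own risks.** This also stands. The documents give no basis for choosing a covariance structure. Year-2 visit timing follows macular fluid, which would not be in the model. A reader might infer that one particular set of time points and covariance parameters is needed or proven; no such claim is made here.

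**Conclusion.** The point holds as a recommended improvement, with medium confidence. As written, the plan leaves a subject without a week-48 or week-104 BCVA out of that primary comparison and gives no use to the BCVA already collected on that subject.

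Selective loss, if it occurs, makes within-cohort mean changes too favourable even when it is equal across cohorts. It biases the cohort difference only when it is unequal. The sizes in letters rest wholly on the assumed SD, correlation and withdrawal pattern. They range from minor (moderate case) to about two-thirds of a standard error (extreme case) and do not predict what happened in this trial. The case for change rests on the low cost of a method that uses data already in hand, not on demonstrated bias.

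**What to change.** **In SAP 6.1**, make the primary BCVA analysis a prespecified likelihood-based (REML) repeated-measures model:
- Include all post-baseline BCVA of all randomised subjects, adjusted for baseline letters and the 20/50 randomisation stratum.
- Fix in advance a small mean structure and covariance suited to 40 subjects, with a variance that may change over time, and use Kenward-Roger degrees of freedom. One example is cohort means joined linearly at weeks 4, 24, 48, 78 and 104 (3 × 5 = 15 means) with a four-parameter covariance; other compact choices would serve.
- From it take an overall A vs B vs C test and Bonferroni-corrected pairwise contrasts at weeks 48 and 104.
- Enter early-termination and year-2 BCVA at the time measured. Do not carry a value to a distant visit.

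**Sensitivity analyses.** Keep the available-case ANOVA. Add one simple shift analysis that lowers the predicted values of subjects withdrawn for adverse events or worsening, for instance by 5, 10 and 15 letters, reported as a range. This one needs a matching exception in Protocol 4.8.4; the main model needs none.

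**Wording.** Reconcile the SAP 6 sentence on data for all 40 with Protocol 4.5.2 and 4.6.

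**Cost.** SAP text, one model and a one-line protocol exception; no new visits or data. The downsides are:
- Software beyond the Prism and Excel named in SAP 2.1.
- Sensitivity to the covariance choice in a small sample. In simulations with arms of 8, 16 and 16 and a single fixed year-2 schedule, a constant-variance covariance gave 95% intervals that covered only 91 to 93% when the SD rose up to week 48.
- Year-2 visit timing that depends on macular fluid.
- Residual bias if loss depends on unobserved acuity.

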4.8.5. Interim Analyses

No formal schedule of interim analyses is planned. Reports of adverse events from this study may be reviewed and summarized periodically while the study is ongoing to ensure the safety of subjects.

4.9. DATA QUALITY ASSURANCE

Accurate, consistent, and reliable data will be ensured through the use of standard practices and procedures.

5. ASSESSMENT OF SAFETY

Specification of Safety Variables

Safety assessments will consist of monitoring and reporting adverse events (AEs) and serious adverse events (SAEs) that are considered related to {study drug}, all events of death, and any study specific issue of concern.

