5.1. ADVERSE EVENTS

An AE is any unfavorable and unintended sign, symptom, or disease temporally associated with the use of an investigational medicinal product (IMP) or other protocol-imposed intervention, regardless of attribution.

This includes the following:

- AEs not previously observed in the subject that emerge during the protocol-specified AE reporting period, including signs or symptoms associated with radiation retinopathy that were not present prior to the AE reporting period.
- Complications that occur as a result of protocol-mandated interventions (e.g., endophthalmitis).

Preexisting medical conditions (other than the condition being studied) judged by the investigator to have worsened in severity or frequency or changed in character during the protocol-specified AE reporting period.

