5.2. METHODS AND TIMING FOR ASSESSING AND RECORDING SAFETY VARIABLES

The investigator is responsible for ensuring that all AEs and SAEs that are observed or reported during the study are collected and reported to the FDA, appropriate IRB(s), and Genentech, Inc. in accordance with CFR 312.32 (IND Safety Reports).

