5.2.1. Adverse Event Reporting Period

The study period during which all AEs and SAEs must be reported begins after informed consent is obtained and initiation of study treatment and ends 28 days following the last administration of study treatment or study discontinuation/termination, whichever is earlier. After this period, investigators should only report SAEs that are attributed to prior study treatment.

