5.2.2. Assessment of Adverse Events

All AEs and SAEs whether volunteered by the subject, discovered by study personnel during questioning, or detected through physical examination, laboratory test, or other means will be reported appropriately. Each reported AE or SAE will be described by its duration (e.g., start and end dates), regulatory seriousness criteria if applicable, suspected relationship to ranibizumab (see following guidance), and actions taken.

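### Protocol Section 5 filters adverse events by relatedness to an unnamed drug, against the all-event rules elsewhere, and causality is recorded for ranibizumab only

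*Protocol*

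**What the plan says.** Under the label for specification of safety variables, Protocol Section 5 lists three things to be monitored and reported: "adverse events (AEs) and serious adverse events (SAEs) that are considered related to {study drug}, all events of death", and then a third, open category. The end of the sentence reads "all events of death, and any study specific issue of concern". The third category is not defined anywhere.

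The subsections that follow set a different scope:

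- Section 5.1 defines an adverse event as one associated with the investigational product "or other protocol-imposed intervention, regardless of attribution", and lists complications of mandated interventions as adverse events.
- Section 5.2 makes the investigator responsible for ensuring that "all AEs and SAEs that are observed or reported during the study are collected and reported to the FDA", the ethics board and the manufacturer.
- Section 5.2.1 opens: "The study period during which all AEs and SAEs must be reported begins after informed consent is obtained". Relatedness matters there only after the reporting period, and only for SAEs.
- Section 5.2.2 covers "All AEs and SAEs whether volunteered by the subject, discovered by study personnel during questioning" or found by other means.

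SAP 6.1 then says: "Adverse events will be reported using counts and percentages for each cohort".

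**The concern.** The paragraph that names the safety variables is where a reader looks for the scope of collection, and it applies a relatedness filter that the operative subsections do not. Taken alone, its first clause would leave out events attributed to the laser, to the underlying disease or to intercurrent illness.

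Laser is the randomized component that separates Cohorts B and C from Cohort A. The design sections describe neither masking nor sham laser, and under Appendix C the treating investigator applies it. (The safety-report template in Appendix G mentions a study blind, but no masking procedure is given.) A filter based on relatedness would therefore be applied by someone who knows the arm. With four sites, different readings of the two rules would make the by-cohort counts depend partly on which site enrolled whom.

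**Working it through.** The point rests on text, and the plan gives no figure to reproduce. The check sets the rules side by side and follows one type of event through them.

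**Step 1: the scope rules in the Protocol.**

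| Place | Scope | Relatedness filter? |
|---|---|---|
| Section 5, opening | Drug-related AEs and SAEs; deaths; study-specific concerns | Yes, for AEs and SAEs |
| 5.1 | Events with the product or any imposed intervention | No |
| 5.2, 5.2.1, 5.2.2 | All AEs and SAEs in the reporting period | No |
| 4.8.2 | Any adverse events, all 40 subjects | No |
| 5.6.1 | Related and unrelated SAEs within 24 hours; special-interest events whatever the cause; non-serious events quarterly | No |
| Appendix A, note 2 | AEs from consent to early termination or study end | No |

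The opening of Section 5 is the only outlier. Its separate mention of deaths suggests that the filter was meant literally: if all events were in scope, deaths would not need listing.

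**Step 2: a laser complication under each rule.**

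- Under 5.1 and 5.2 it is an adverse event and is recorded, because TRP is an intervention that the protocol imposes.
- Under Section 5 the first question is whether it is drug-related. Section 5.5.2.9 answers No when there is evidence of a cause other than ranibizumab. The event then fails the first clause and enters only if it is fatal or if the site treats it as a study-specific concern.
- Some laser events could still be judged Yes. The Yes criteria are joined by and/or, and the first TRP session comes about one week after the first injection.

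**Step 3: attribution.** Protocol 3.4, repeated in SAP 4.3, has every adverse event reviewed for relationship to the study drug and/or study procedures. The relationship described for each event in 5.2.2 is to ranibizumab, and the guideline in 5.5.2.9 is written for ranibizumab only. So even with complete capture, the protocol sets no item or rule for marking an event as laser-related.

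**Step 4: the placeholder.** The unfilled drug field is also in 5.5.2.5 (congenital anomaly) and 5.5.2.6 (post-study SAEs). Neighbouring sections name ranibizumab.

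**Step 5: how many subjects are exposed to laser.**

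- Planned sizes (Protocol 3.2): Cohort B 16 + Cohort C 16 = 32; 32/40 = 80%.
- Subjects with 20/50 or better are randomized 1:1:1 (Protocol 4.2). If all 40 fell in that stratum, the expected number would be 40 × 2/3 = 26.7, or 67%.
- The expected number assigned to laser therefore lies between about 27 and 32.

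The documents give no laser complication rate, so no number of lost events can be derived.

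**The case against.** The strongest defence is that the Section 5 sentence is leftover template text and every working rule overrides it. Most of this stands. Sections 5.1 to 5.2.2, 4.8.2, 5.6.1 and Appendix A all point the same way. Retinal detachment and marked intraocular inflammation are on the special-interest list in 5.5.2.8, so they go to the manufacturer whatever their cause. Ranibizumab is the only study drug, so the blank field misleads nobody in practice. SAP 6.1 promises only counts and percentages by cohort, not a formal laser versus no-laser comparison of adverse events.

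Three stronger readings are tempting, and the documents do not support them.

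- A reader might infer that Section 5 confines monitoring to drug-related events plus deaths. It does not: the sentence has a third category that could take in laser events.
- A reader might infer that laser events fall outside the protocol's safety scope. Sections 5.1 and 3.4 bring them in.
- A reader might infer that almost no laser events would be captured. That requires every site to follow one clause of Section 5 against all the collection rules, never to use the third category, and never to judge a laser event drug-related.

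The defence does not remove the contradiction. The third category is undefined and gives a site no rule to apply. Nor does it answer the attribution gap, which exists even if every event is recorded.

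**Conclusion.** The contradiction is real and can be read directly from the current text: Section 5 filters AEs and SAEs by relatedness to an unnamed drug, and the rest of the Protocol does not. The likely loss of data is small, on the assumption that sites follow 5.1 to 5.2.2. If a site applied the Section 5 filter instead, it would under-record non-drug events. Laser-attributed losses would fall only in Cohorts B and C, so they would make the laser arms look safer relative to Cohort A.

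The clearer laser gap is in attribution: Protocol 3.4 promises causality review against study procedures, but 5.2.2 and 5.5.2.9 provide for ranibizumab alone. No endpoint, analysis set or sample size is affected. This is a minor reconciliation of conflicting passages.

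**What to change.** 1. Reword the scope sentence in Protocol Section 5 to cover all AEs and SAEs regardless of attribution to ranibizumab, the injection procedure or TRP, together with all deaths and the special-interest events in 5.5.2.8. Define the study-specific category or delete it.
2. Fill the drug field in Sections 5, 5.5.2.5 and 5.5.2.6.
3. Extend the relationship item in 5.2.2 and the guideline in 5.5.2.9 to record relationship to study procedures, including TRP, as 3.4 already states.
4. If data collection has ended (parts of the SAP are in the past tense), state in the SAP which capture rule the sites applied. Check by site that the adverse event listing contains events judged unrelated to ranibizumab. If a site has none, say so beside the cohort table.

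Items 1 and 2 are wording only and add no collection, since 5.2 already requires it. Item 3 may need one or two extra fields on the adverse event form, which is not among the documents. Item 4 is a short listing review.
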